### 8.3 Statistical methods

If at least one of the two cultures from a shoulder turns positive, that shoulder will be counted as a “positive culture” shoulder. The results of the two cultures from each shoulder will be McNemar test will be used to compare the proportions of positive culture rates between paired shoulders. Ordinal or interval Demographic data will be compared between the two groups using parametric vs nonparametric tests depending on their normality. Nominal data will be compared using Fisher’s exact test or contingency table. The negative control data will be analyzed in comparison to the results of the treatment and normal control shoulders.

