At the time of the surgery, 2 separate 3-mm punch biopsy specimens will be taken from the posterior shoulder skin of both shoulders using a disposable biopsy punch (Disposable Biopsy Punch; Robbins Instruments, Chatham, NJ, USA) (Figure 2) . The biopsy sites will be closed with an adhesive tape (Steri-Strip, 3M, Maplewood, MN, USA) and covered with a routine gauze dressing. Samples will be transferred directly into separate sterile specimen containers from the biopsy punches using clean, sterile forceps. Specimens will then be transferred directly to a single laboratory for culture. Anaerobic and aerobic culture substrates will be used and held for 14 days for *P. acnes* only, given literature that shows *P. acnes* can grow on either substrate. Anaerobic culture plates will be incubated for 4 days and broth cultures for 14 days before concluding that the final report is negative. To serve as a “negative control,” while wearing sterile gloves, in the first 20 patients, a sterile culture swab will be opened in the operating room, wiped through the air, and sealed in a specimen container. Chocolate plate will serve as a settle plate in the OR suite for 10 minutes and incubated for 4 days. Data will include demographic data of patients, positive culture rates, and the number of days before resulting in positive culture. All culture results will be reviewed and the patient will be marked positive if any of the cultures were positive. Patients will be scheduled for postoperative, routine follow-up visits. The rest of patient care will follow our current routine standard care without any modifications or interventions.

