**8.2 Sample size determination**

A priori sample size calculation was performed using some of the previously published data. Assumptions were made as follows: the primary outcome measure was the intraoperative culture results (e.g. positive, negative) for *P. acnes* by evaluating bacterial cultures from two skin biopsies obtained from the posterior aspect of the shoulder at the time of the surgery. Based on a previous study, the positive culture rate in untreated shoulders was set at 60%. We set the minimally clinically significant difference (MCID) of positive culture rate at 30% (a half of 60%) as a previous study described. Using a two-tailed McNemar test for two dependent groups with a power of 0.8 and an alpha of 0.05, the priori sample size calculation suggested a total of 30 patients for the study.

Probability		Treatment shoulder		
		Positive culture	Negative culture	
Control shoulder	Positive culture	0.25	0.35	0.6
	Negative culture	0.05	0.35	0.4
		0.3	0.7	1

Exact - Proportions: Inequality, two dependent groups (McNemar)

Options:  $\alpha$  balancing:  $\alpha/2$  on each side, approximation

Analysis: A priori: Compute required sample size

Input: Tail(s) = Two

Odds ratio = 7

$\alpha$  err prob = 0.05

Power (1- $\beta$  err prob) = 0.8

Prop discordant pairs = 0.4

Output: Lower critical N = 2.000000

Upper critical N = 10.000000

Total sample size	=	30
Actual power	=	0.8180007
Actual $\alpha$	=	0.0385742
Proportion p12	=	0.3500000
Proportion p21	=	0.0500000

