### 10.7 Statistical tests

The proportion of positive cultures will be determined using Fisher’s exact test to compare the positive culture rates. Ordinal or interval Demographic data will be compared between the two groups using parametric vs nonparametric tests depending on their normality. Nominal data will be compared using Fisher’s exact test or contingency table.

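### The primary comparison is planned as a McNemar test with no paired difference, discordant counts or confidence interval, so a non-significant result cannot be read against the plan's own 30-point difference

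*Combined protocol and SAP*

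**What the plan says.** Section 8.3 of the combined protocol and SAP classifies each shoulder ("If at least one of the two cultures from a shoulder turns positive", it counts as positive) and then names the comparison: "McNemar test will be used to compare the proportions of positive culture rates between paired shoulders". No effect measure or interval follows.

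Section 10.7 covers the same comparison with a different, unpaired test, Fisher's "exact test to compare the positive culture rates", again with no estimate.

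Section 8.2 supplies the benchmark. It says that "the positive culture rate in untreated shoulders was set at 60" percent and "We set the minimally clinically significant difference (MCID) of positive culture rate at 30" percent, meaning a fall from 0.60 to 0.30. The calculation is described as "Using a two-tailed McNemar test for two dependent groups with a power of 0.8 and an alpha of 0.05".

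Section 7.1 comes closest to a reporting commitment: "Data will include demographic data of patients, positive culture rates, and the number of days before resulting in positive culture". Section 1.3 lists no secondary endpoints. No section mentions a confidence interval.

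**The concern.** The plan states which difference matters but plans no quantity that can be compared with it. A significant result would at least come with two marginal rates. A non-significant result is harder to use: the reader needs to know whether a 30-point reduction is still plausible or has been ruled out, and the p-value does not say.

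The marginal rates do not fill the gap. The precision of a paired difference depends on the two discordant counts, and different discordant counts can lie behind the same pair of marginal rates. With only 30 pairs and one main efficacy comparison, nothing else in the plan would show that a result was inconclusive.

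**Working it through.** **Inputs (section 8.2).** N = 30 pairs; probability of control positive and treatment negative, p12 = 0.35; probability of the reverse, p21 = 0.05; discordant proportion 0.40; two-sided alpha 0.05. Let b be the number of discordant pairs favouring treatment and c the number favouring control. The paired difference is d = (b − c)/30.

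**The plan's own figure.** The output fixes the discordant pairs at 30 × 0.40 = 12. With 0.35/0.40 = 0.875 and critical values 2 and 10, P(X ≥ 10 | 12, 0.875) = 0.818, and the actual alpha is 2 × P(X ≤ 2 | 12, 0.5) = 0.0386. Both match section 8.2.

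**Precision at the planned effect.** SE(d) = √[(0.40 − 0.30²)/30] = √(0.31/30) = 0.102, so a 95% interval extends about ±20 points.

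**Interval used.** The Tango score limits solve T(D) = ±1.96, where T(D) = (b − c − nD)/√{n[2q + D(1 − D)]}, q = [√(B² − 4AC) − B]/(2A), A = 2n, B = −b − c + (2n − b + c)D and C = −cD(1 − D).

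| b v c | d (points) | exact p | 95% limits (points) | 30 points |
|---|---|---|---|---|
| 8 v 3 | 16.7 | 0.23 | −5.5 to 37.6 | included |
| 3 v 0 | 10.0 | 0.25 | −2.5 to 25.6 | excluded |
| 8 v 4 | 13.3 | 0.388 | −9.9 to 35.3 | included |
| 4 v 8 | −13.3 | 0.388 | −35.3 to 9.9 | excluded |

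Check of the 3 v 0 upper limit: c = 0 gives q = 0. At D = 0.256, (3 − 7.69)/√(30 × 0.256 × 0.744) = −4.69/2.39 = −1.96.

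The first two rows favour the same shoulder and have nearly equal p-values, but differ on whether 30 points remains plausible. The uncorrected asymptotic test does not help. It gives (8 − 3)²/11 = 2.27 (p = 0.13) and 3²/3 = 3.00 (p = 0.083), so the smaller p-value belongs to the result that excludes 30 points.

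**How often it matters.** All (b, c) outcomes for N = 30 were enumerated with trinomial probabilities.

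- Planned effect true (0.35, 0.05): 28.7% of trials are non-significant with the exact test and 20.5% with the uncorrected asymptotic test.
- No effect, discordance 0.40 (assumed; 0.20, 0.20): 97.6% are non-significant by the exact test. The interval includes 30 points in 25.6% of these and excludes it in 74.4%.
- No effect, discordance 0.20 (assumed; 0.10, 0.10): 98.7% are non-significant by the exact test. The interval includes 30 points in 7.5% of these and excludes it in 92.5%.

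**Agreement of test and interval.** The Tango interval inverts the uncorrected asymptotic test, not the exact one. For 7 v 1, exact p = 0.070 but the limits are 1.9 to 38.6. For 5 v 0, exact p = 0.0625 but the limits are 3.4 to 33.6. At the planned effect, exact p > 0.05 with an interval that excludes zero occurs in 8.1% of trials.

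**The case against.** The strongest reply is that this is a reporting gap and not a design fault. Section 8.3 names a test without limiting the report to a p-value. Section 7.1 lists positive culture rates, so the crude difference and its direction will be available, and the paired table yields an interval afterwards with no new data. That stands, and it limits the point to what the plan commits to. It does not remove the point, because the discordant counts are not promised and the rule for reading a null result should be fixed before the data are seen.

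A reader might infer that the investigators intend to treat p > 0.05 as proof of no efficacy. The documents contain no rule for null results, so that reading is not supported.

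A reader might also rely on the fact that, under the planned effect, the interval includes 30 points in 92% of non-significant (exact) trials (26.4% of all trials). That figure largely restates 95% coverage of a true 30-point difference. The evidence that the interval discriminates comes from the no-effect cases and the paired examples.

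Section 8.3 does not say which McNemar version will be used. The exact form appears only in the sample-size output, so 28.7% is one end of a range. The sentence before the test in section 8.3 is also broken, and some text on summarising results may have been lost. That is no evidence that an interval was planned.

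**Conclusion.** The point holds as a gap in the planned analysis and reporting. No section commits to a paired difference, discordant counts or an interval, and at 30 pairs the p-value alone does not show whether the 30-point difference has been excluded. A non-significant result is a realistic prospect even if the planned effect is real: 20.5% to 28.7% of trials, depending on the McNemar version. If there is no effect, an interval would turn about 74% of non-significant trials into evidence against 30 points at 40% discordance, and about 92% at 20%. Both discordance values are assumptions for the null case, and both percentages use the exact test with Tango limits.

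A reader might go further and infer that the trial is unable to tell these results apart, or that the test is invalid. Neither follows. The paired table that the trial will collect contains the information, and the McNemar test suits the paired design.

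**What to change.** In section 8.3:

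1. Name the McNemar version, exact or uncorrected asymptotic, and amend section 10.7 so that both sections give the same paired test.
2. Report the paired 2×2 table and the paired difference in positive-culture proportions with a 95% interval consistent with that version: Tango score with the uncorrected asymptotic test, or an exact interval with the exact test.
3. State that if test and interval disagree, the test decides significance and the interval is for estimation.
4. State that a non-significant result is reported as inconclusive about the planned effect when the interval includes a 30-point reduction, and as evidence against it only when the upper limit is below 30 points.

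The cost is a few sentences and minutes of analysis, with no extra patients, specimens or data. The one statistical price is that an exact interval would be slightly wider than the score interval.

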### 7.4.4 Subject Compliance Monitoring

### 7.4.5 Blinding of the Test Article

N/A

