## 10.0 Data and Safety Monitoring Plan

### 10.1 Periodic evaluation of data

Data will be reviewed periodically by the PI for the accuracy during the data collection period.

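### Does the missing rule for a positive negative-control swab put the primary McNemar comparison at risk?

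*Combined protocol and SAP*

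**What the plan says.** Section 7.1 describes the control, which is limited to the 20 patients enrolled earliest: "a sterile culture swab will be opened in the operating room, wiped through the air, and sealed in a specimen container". It then adds a chocolate settle plate, exposed for 10 minutes and incubated for 4 days. The 4-day plate and 14-day broth times come earlier, in the text on the biopsies, and no medium or hold time is attached to the swab. Shortly afterwards 7.1 states: "All culture results will be reviewed and the patient will be marked positive if any of the cultures were positive".

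Section 8.3 covers the analysis of the control in one sentence: "The negative control data will be analyzed in comparison to the results of the treatment and normal control shoulders". The same section defines the unit that enters the McNemar test. A shoulder counts as positive on this condition: "If at least one of the two cultures from a shoulder turns positive". Sections 1.2 and 8.2 likewise define the primary outcome by cultures of skin biopsies.

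Section 10.7, the other statistical passage, does not mention the control. The entry under "Blinding of the Test Article" (7.4.5) is not applicable, and section 10.1 says: "Data will be reviewed periodically by the PI for the accuracy during the data collection period".

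**The concern.** A negative control is taken so that something can be concluded from it, and the plan does not say what. If a patient's swab grew *P. acnes*, the analyst could keep the pair, drop the patient, mark the patient positive under the broad sentence in 7.1, or call the shoulder growth contamination. Each of the last three could take a discordant pair out of the McNemar count, and that test uses discordant pairs only.

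The sample size output expects few of them ("Prop discordant pairs = 0.4", so 12 of 30) and sets a high bar ("Upper critical N = 10.000000"). One pair could therefore decide significance. The trial is unblinded and the principal investigator sees data as they accrue, so the choice might be made with the shoulder results in view. The settle plate's status as a control is also open. A swab not held in 14-day broth could not speak to shoulder cultures that turn positive late.

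**Working it through.** **Inputs.** From 8.2: 30 pairs; p12 = 0.35 (control shoulder positive only); p21 = 0.05 (treatment shoulder positive only); discordant proportion 0.40; two-sided alpha 0.05. From 7.1: swabs in 20 patients. The swab-positive rate r is not in the documents, so I assume 1%, 5% or 10%, independent of the shoulder results.

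**1. The plan's own figures.** Expected discordant pairs are 30 × 0.4 = 12, and the chance that one favours treatment is 0.35/0.40 = 0.875.
- Actual alpha: 2 × P(X ≤ 2 | 12, 0.5) = 2 × 79/4096 = 0.0386. The plan gives 0.0385742.
- Power: P(X ≥ 10 | 12, 0.875) = 0.8180. The plan gives 0.8180007.

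**2. One pair at the boundary** (exact two-sided p).
- 10 v 2: 0.0386.
- 9 v 2: 2 × 67/2048 = 0.0654.
- 10 v 3: 2 × 378/8192 = 0.0923, which becomes 0.0386 if one of the 3 is removed.

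So removing a pair can change the conclusion in either direction, for results that sit at the boundary.

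**3. Power with fewer pairs.** On the plan's fixed-count basis:

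| Discordant pairs | Needed in one direction | Alpha | Power |
|---|---|---|---|
| 12 | 10 | 0.0386 | 0.818 |
| 11 | 10 | 0.0117 | 0.592 |
| 10 | 9 | 0.0215 | 0.639 |
| 9 | 8 | 0.0391 | 0.687 |

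The fall from 12 to 11 pairs looks severe, but power then rises as more pairs are lost. The drop comes from the discreteness of the test and does not measure the loss of information.

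**4. Power with the number of discordant pairs random.** I let that number follow Binomial(N, 0.4) and dropped every swab-positive patient among the 20.

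| r | Chance of ≥1 positive swab, 1 − (1 − r)^20 | Chance of ≥1 in a discordant pair, 1 − (1 − 0.4r)^20 | Exact power | Trials where the p < 0.05 conclusion differs |
|---|---|---|---|---|
| 0 | 0 | 0 | 0.713 | 0 |
| 1% | 18% | 8% | 0.709 | 0.8% |
| 5% | 64% | 33% | 0.693 | 3.7% |
| 10% | 88% | 56% | 0.671 | 7.0% |

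The cost is 0.4 to 4.2 percentage points (0.713 − 0.709 to 0.713 − 0.671), and only under an exclusion that the plan does not contain.

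**5. Can the sentence in 7.1 feed the test?** It marks the patient. McNemar compares two shoulders within a patient. If a patient-level mark were carried over, one positive biopsy on either side would make both shoulders positive and every discordant pair would disappear, whatever the swab showed. That reading leaves no primary analysis at all, so it cannot be the intended one. The shoulder rule in 8.3 is the only workable definition, and it uses that shoulder's two cultures.

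**6. If swabs are ignored and contamination is real.** Suppose contamination at rate c strikes each shoulder independently. The expected difference becomes 0.30 × (1 − c): 0.285, 0.27 or 0.24 at c = 5%, 10% or 20%. Equal contamination of both shoulders shrinks the effect and does not create one.

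**The case for a change.** The strongest case for a change is that the plan collects a control, promises to analyse it, and leaves open the decision a control exists to inform. In an unblinded trial with a boundary at 10 of 12, a few words now would remove a choice that could later decide significance. No patient would undergo anything extra.

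The factual part of this stands. Section 8.3 gives neither a test nor a consequence, 7.1 does not say how the swab is cultured, and its patient-level sentence is loose. The general line in 8.3 on nominal data (Fisher's exact test or contingency table) might supply a test, but it follows the demographic comparisons and still gives no consequence. A negative result will also say little: 0 of 20 excludes only rates above 1 − 0.05^(1/20) = 13.9% (one-sided 95%).

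The link to the primary result does not stand. Dropping or recoding a pair because of a swab would depart from the written shoulder rule. Section 10.1 has the investigator check accuracy and gives no authority to rule on contamination. Nor is the control unnamed, since 7.1 applies that label to the swab; only the settle plate is unclear.

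**Conclusion.** No change follows. This is missing detail in a descriptive contamination check, and an analyst would fill it sensibly: keep every pair, score each shoulder from its two biopsies, and report swab positives as a count out of 20 with an exact interval. A rule saying that swabs neither exclude nor reclassify a shoulder would repeat what 8.3 implies. A sensitivity analysis without swab-positive patients and a note on swab culture are optional and would not alter the primary result.

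Followed as written, the plan lets the swab have no effect on the McNemar test. If it were departed from by dropping every swab-positive pair, the loss would be at most about 4 points of power, and the conclusion would differ in at most 7.0% of trials, for swab-positive rates up to 10%. Those figures rest on the plan's own 2×2 table, the assumed rates, and independence of swab and shoulder results. They use McNemar as in 8.2 and 8.3; the different test named in 10.7 is a separate matter.

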## 9.0 Confidentiality, Privacy and Data Management

See the Research Data Plan Review Form.

## 10.0 Data and Safety Monitoring Plan

### 10.1 Periodic evaluation of data

Data will be reviewed periodically by the PI for the accuracy during the data collection period.

### 10.2 Data that are reviewed

Previously stated data will be secured with password protection. Staff members will periodically review safety and security protocols for project.

### 10.3 Method of collection of safety information

The duration of the post-operation routine care follow-up can take place between a few weeks to several months depending on the procedure. The culture results will be obtained within 14 days post-operation. Any change in the condition of the biopsied area will be recorded and followed, including infections, as part of the routine care visits.

### 10.4 Frequency of data collection

The skin biopsies will be obtained only at the time of surgery. The biopsies will be sent to the microbiology lab for cultures. The culture results will be obtained within 14 days post-operation. No further follow up data collection will be performed directly from patients after their surgery.

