### 7.2.2 Post-operation

Patients will follow our current routine standard care follow-up protocol for each surgical procedure. The biopsy sites will be carefully examined by the PI or his patient care team to ensure proper healing upon each postoperative return visit. The first postoperative visit is at 2 weeks after surgery. Any wound problems such as bleeding, drainage, abnormally increased pain, feeling of local warmth, erythema, and abnormal swelling will be immediately reported to the PI or his patient care team. The duration of the post-operation routine care follow-up can take place between a few weeks to several months depending on the procedure. The culture results will be obtained within 14 days post-operation. Any change in the condition of the biopsied area will be recorded and followed, including infections, as part of the routine care visits.

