### 10.6 Frequency of review of cumulative data

Cumulative data will be reviewed once patient surveys are collected and patient information is de-identified.

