##### **20.1.2 Safety Monitoring**

N/A

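### Sections 10.4 and 10.6 leave biopsy-site harms with no stated route into the study data and no cumulative review that can take place as written

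*Combined protocol and SAP*

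**What the plan says.** All references are to the combined protocol and SAP.

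- **Recording of harms.** Section 10.3, the safety collection method, says: "Any change in the condition of the biopsied area will be recorded and followed, including infections, as part of the routine care visits". Sections 1.2, 7.2.2 and 7.3 make the same promise; 1.2 places it under the primary endpoint heading. Section 7.2.2 adds: "The biopsy sites will be carefully examined by the PI or his patient care team to ensure proper healing upon each postoperative return visit". It also gives the timing: "The first postoperative visit is at 2 weeks after surgery".
- **Frequency of data collection.** Section 10.4 says: "No further follow up data collection will be performed directly from patients after their surgery".
- **Content of the study data.** Section 7.1 says: "Data will include demographic data of patients, positive culture rates, and the number of days before resulting in positive culture". Section 8.3 covers culture comparisons, demographics and the negative control, and mentions no harms.
- **Review.** Section 10.6 says: "Cumulative data will be reviewed once patient surveys are collected and patient information is de-identified". Section 10.1 says: "Data will be reviewed periodically by the PI for the accuracy during the data collection period". Section 10.5 says only that research members review data. The section headed "20.1.2 Safety Monitoring" is answered N/A.
- **Suspension.** Section 10.8 suspends the research if it is found unsafe, and attaches no schedule of review.

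**The concern.** Section 10.4 is the rule on when data are collected. On its face it excludes what four other sections promise, because every routine postoperative visit comes after surgery. A coordinator building the study form from 7.1 and 10.4 would have no reason to include a biopsy-site field.

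Section 10.6 is the only rule on cumulative review, and it waits for something this study does not produce.

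The punch biopsies are made for the study's cultures, and half of them are on a shoulder that has no operation. A reader of the results would expect a count of biopsy-site problems per shoulder. The team would also want to notice a run of minor problems while enrolment is still open. As written, the plan secures neither.

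**Working it through.** The plan states no figure for harms, so this is mainly a comparison of text. The only design figure used is the sample size of 30 (8.1). It reproduces from the inputs in 8.2: with 30 x 0.4 = 12 discordant pairs, rejection at 2 or fewer or 10 or more, and 0.35/0.40 = 0.875 as the chance that a discordant pair favours treatment, power is 0.8180 and alpha 0.0386, as stated. The point does not depend on this calculation.

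**Step 1: 10.4 against 10.3.** Sections 1.2, 7.2.2, 7.3 and 10.3 require biopsy-site findings to be recorded at visits from 2 weeks onward. Section 10.4 ends collection directly from patients at surgery. Two readings are possible.

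- *Literal reading:* no follow-up data come from patients after surgery. This contradicts the four sections.
- *Narrow reading:* there is no research-only contact, and findings come from routine-care records. This removes the contradiction, but a sentence is then needed to move clinic findings into the study data. Section 7.1 does not list them, and 8.3 does not summarise them.

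Either reading calls for an edit.

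**Step 2: the trigger in 10.6.** Review follows collection of patient surveys. No other section mentions a survey, and none appears in the data list in 7.1. The condition is never met.

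**Step 3: whether another section supplies a cumulative review of harms.**

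| Section | What it provides | Cumulative harm review? |
|---|---|---|
| 10.1 | Periodic review by the PI, for accuracy | No |
| 10.2 | Password protection; staff review of safety and security protocols | No |
| 10.5 | Who reviews data, not which data or when | No |
| 16.5 | Monthly meetings to review protocols | No |
| 19.2, 19.3 | Follow-up and causality of single events, judged against drug or device | No |
| 19.5 | IRB reports of single harms that are unexpected and probably related to research procedures | No |
| 20.1.2 | N/A | No |

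Section 19 also fits the biopsies loosely. A punch wound is a research procedure, not the device, so the causality wording in 19.2 and 19.3 does not clearly reach it. Section 19.5 does cover research procedures, but only for unexpected harms. Section 11.0 already lists bleeding, pain, infection, scarring and healing problems as possible biopsy risks, so events of those kinds would usually count as expected.

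**Step 4: scale.** Inputs are 30 patients (8.1) and 2 punches in each of 2 shoulders (7.1).

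- Biopsy wounds: 30 x 2 x 2 = 120.
- On the non-operative shoulder: 30 x 2 = 60.

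**Step 5: what recording would allow.** If all 30 patients were assessed and none had an event, the upper bound on the per-patient rate would be:

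- one-sided 95%: 1 - 0.05^(1/30) = 0.095, or 9.5%;
- upper limit of a two-sided 95% interval: 1 - 0.025^(1/30) = 0.116, or 11.6%.

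The patient is the unit here because the four wounds in one patient are not independent. Zero events is an illustration, not a forecast. These bounds describe what a sample of 30 can say; they do not measure the defect.

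**The case against.** The strongest reply is that the plan does look for harms. Section 10.4 limits only collection made directly from patients, and four sections say in plain terms that biopsy-site changes are recorded at routine visits. Section 7.2.2 has the sites examined at every return visit and has wound problems reported at once to the PI or care team. Section 19 adds prompt review of documented events and a route to the IRB. In a study of 30 patients under one PI, that may seem enough.

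Much of this stands, and it rules out three stronger conclusions that a reader might draw.

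- *That biopsy-site harms are not captured.* Sections 7.2.2 and 10.3 provide for examination and recording in clinic. What is missing is the step from the clinic record to the study data.
- *That the suspension rule in 10.8 has nothing to act on.* A single event seen under 7.2.2 or reviewed under 19.3 could prompt suspension at any time. What 10.8 lacks is a cumulative input.
- *That 10.4 prevents a dressing complication rate.* The dressing is worn before surgery and comes off on transfer to the operating room (7.1), and 10.4 restricts only collection after surgery. Section 19.7 also tells patients to consult the PI about skin reactions. It remains true that 7.1 lists no field for such reactions.

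The reply does not rescue 10.6. No reading of the plan gives the study a patient survey, and event-by-event handling does not replace looking at the events together.

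**Conclusion.** The point holds as two wording defects with a practical consequence. First, 10.4 conflicts on its face with 1.2, 7.2.2, 7.3 and 10.3; on its kinder reading, no section brings routine-visit findings into the study data or plans a summary of them. Second, the trigger in 10.6 cannot occur, and no other section provides a cumulative review of harms. Taken as written, harms from 120 research biopsy wounds, 60 of them on a non-operative shoulder, are dealt with singly and never together, and the trial has no planned basis for reporting a rate.

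The primary comparison of culture results is unaffected. The change should be made, but the point does not show that patients go unexamined.

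The conclusion rests on the text available. Section 9.0 refers to a separate data plan form that is not part of it. If that form already holds a biopsy-site field, the first defect shrinks to reconciling 10.4 and 7.1 with it; the second is unchanged.

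**What to change.** 1. **Section 10.4.** Say that there are no research-only visits after surgery, but that biopsy-site status for each shoulder will be entered on the study form from the existing 2-week visit, and from later routine visits if a problem is noted. Naming each shoulder matters because routine follow-up centres on the operated one. Dressing-site reactions should be entered at dressing removal on the day of surgery, close to the exposure.
2. **Sections 7.1 and 8.3.** Add these items to the data list and state that both will be reported descriptively: counts of patients with events, by shoulder for the biopsy sites, with an exact confidence interval.
3. **Section 10.6.** Replace the survey trigger with one that occurs, such as PI review of cumulative biopsy-site and dressing events at stated points during enrolment, with the result feeding 10.8. The interval is the sponsor's choice. No stopping threshold is proposed here.

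The cost is a few sentences, a short form entry at contacts that already take place, and a small data-entry effort. No visit, procedure or element of care changes.
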